3.3.5. Desirability Of Outcome Ranking (DOOR)

DOOR is defined as follows:

- Each subject is evaluated according to the ordinal clinical outcome (OCO) (See [Table 2](#) below).

- DOOR is then assigned according to two rules:
 - When comparing two subjects with different ordinal clinical outcomes (OCOs), the subject with a better OCO receives a higher rank.
 - When comparing two subjects with the same OCOs, the subject with fewer days of antibiotic use receives a higher rank.

Table 2: Ordinal Clinical Outcomes Assessed at D5V

OCO	Adequate Clinical Improvement* (Assessed at Outcome Assessment Day 5)	Solicited Events** (Assessed through Outcome Assessment Day 5)
1	Yes	None
2	Yes	Mild (Grade 1)
3	Yes	Moderate (Grade 2)
4	Yes	Severe (Grade 3)
5	No adequate clinical improvement with no medically attended events	None or any grade
6	No adequate clinical improvement with ED, outpatient clinic, or urgent care center visit but no hospitalization	None or any grade
7	No adequate clinical improvement with hospitalization	None or any grade
8	Death (any cause)	--
*Clinical improvement as defined in Section 3.3.2. **Solicited events are defined in Table 7.		

Table 3: Ordinal Clinical Outcomes Assessed at D11V

OCO	Adequate Clinical Improvement* (Assessed at Outcome Assessment Day 11)	Solicited Events** (Assessed through Outcome Assessment Day 11)
1	Yes	None
2	Yes	Mild (Grade 1)
3	Yes	Moderate (Grade 2)
4	Yes	Severe (Grade 3)
5	No adequate clinical improvement with no medically attended events	None or any grade
6	No adequate clinical improvement with ED, outpatient clinic, or urgent care center visit but no hospitalization	None or any grade
7	No adequate clinical improvement with hospitalization	None or any grade
8	Death (any cause)	--
*Clinical improvement as defined in Section 3.3.2. **Solicited events are defined in Table 7.		

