3. STUDY OBJECTIVES AND ENDPOINTS

3.1. Study Objectives

3.1.1. Primary:

1. To compare the efficacy of azithromycin versus placebo on Day 5 (i.e., after 4 days of treatment) in subjects with suspect LRTI and PCT levels of ≤ 0.25 ng/mL at enrollment using a non-inferiority approach.

3.1.2. Secondary:

1. To compare groups receiving azithromycin versus placebo with regard to all antibiotic use by Days 11 and 28.
2. To compare groups receiving azithromycin versus placebo with regard to return visits to a physician's office or urgent care by Days 11 and 28.
3. To compare groups receiving azithromycin versus placebo with regard to emergency department visits by Days 11 and 28.
4. To compare groups receiving azithromycin versus placebo with regard to hospitalization by Days 11 and 28 if not hospitalized at the enrollment and randomization visit.
5. To compare groups receiving azithromycin versus placebo with regard to improvement in presenting symptoms by Days 11 and 28.
6. To compare the efficacy of azithromycin versus placebo on Day 11 in subjects with suspect LRTI and PCT levels of ≤ 0.25 ng/mL at enrollment using a non-inferiority approach.
7. To compare the efficacy of azithromycin versus placebo on Day 28 in subjects with suspect LRTI and PCT levels of ≤ 0.25 ng/mL at enrollment using a non-inferiority approach.
8. To compare the efficacy of azithromycin versus placebo in subjects with suspected LRTI and PCT levels of ≤ 0.25 ng/mL at Day 5 using a superiority approach, employing the RADAR methodology.
9. To compare groups receiving azithromycin versus placebo in regard to solicited events by Day 5.
10. To compare groups receiving azithromycin versus placebo in regard to hospitalization or visits to an Emergency Department (ED), outpatient clinic, or urgent care center for worsening or persistent LRTI after randomization by Day 5.
11. To compare groups receiving azithromycin versus placebo in regard to improvement in vital sign abnormalities or symptoms present at enrollment, on Day 5.
12. To compare groups receiving azithromycin versus placebo in regard to new vital sign abnormalities or symptoms on Day 5, or deterioration in symptoms relative to the enrollment visit on Day 5.

3.1.3. Exploratory:

1. To compare PCT levels at Day 1 and Day 5 among treatment failures in the placebo and azithromycin groups.

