4.4. Treatments

4.4.1. Treatments Administered

Azithromycin 500 mg or placebo (administered orally as two 250 mg capsules or two matching placebo capsules) as a single dose on Day 1, followed by Azithromycin 250 mg or placebo (administered orally as one 250 mg capsule or one matching placebo capsule) once daily for 4 days (Day 2 through Day 5).

Capsules should be maintained as dispensed and not scored, cut, crushed, or otherwise divided for ease of swallowing. The capsules will be administered with water sufficient for the subject to swallow the required number of capsules.

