6.5.5. Number of Days of Antibiotic Use at D5V, D11V, or D28V

Analysis involving comparisons of the number of days of antibiotic use will consider all antibiotic use from Day 1 onwards including study antibiotics and non-study antibiotics for systemic use. The number of days of antibiotic use is defined as the actual number of days of antibiotic use (any amount of study product that is not placebo, or any amount of other systemic antibiotic) from Day 1 to D5V study day inclusive for D5V, from Day 1 to D11V study day inclusive for D11V, and from Day 1 through D28V study day inclusive for D28V. For subjects that received placebo as study product, it is counted as the number of days of systemic antibiotic as determined solely from the concomitant medication form. For subjects that receive actual antibiotic as study product, it is counted as the number of days that the subject received any amount of either study product or a non-study systemic antibiotic, as determined from the concomitant medication form. Note that missed doses of study product do not necessarily lower the number of days of antibiotic use as long as a separate dose of antibiotic (study product antibiotic or concomitant medication antibiotic) was received on that day. The number of days of antibiotic use is missing (at D5V, D11V, and D28V) if the product administration record was not completed for the subject and the subject did not have non-study systemic antibiotic use during the study period recorded as a concomitant medication.

The number of days of antibiotic use at the time of analysis will be determined from the product administration records and concomitant medication records only. Data management activities and site queries (outside the scope of this document) prior to data lock will ensure concomitant medication records are as complete as possible and consistent with other records (i.e., AEs and medically attended visit records in the clinical database). The number of days of antibiotic use for a concomitant medication will be calculated as the medication end date minus the medication start date plus one day. Days will not be double counted if multiple systemic antibiotics (including antibiotic as study product) are taken on the same day. Systemic antibiotic use will not be counted for days that fall outside of the range being considered for each subject (Days 1 to D5V study day, or Day 1 to D11V study day, or Day 1 to D28V study day).

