6.5.6. Desirability of Outcome Ranking (DOOR) at D5V or D11V

DOOR at D5V is defined by ranking all subjects (pooling together both treatment arms) according to OCO at D5V (lower is better) and using the number of days of antibiotic use at D5V (lower is better) as a tie-breaker for comparing the ranking of two subjects with the same OCO. DOOR at D11V is defined by ranking all subjects (pooling together both treatment arms) according to OCO at D11V (lower is better) and using the number of days of antibiotic use at D11V (lower is better) as a tie-breaker for comparing the ranking of two subjects with the same OCO. DOOR at D5V or at D11V is missing only if OCO or number of days of antibiotic use is missing for the respective visit.

The ranking algorithm for DOOR is implemented as follows. A score variable is created that adds the number of days of antibiotic use (as defined in Section 6.5.5) divided by 100 to the OCO. Subjects are then ranked

(DOOR) by the score, with the highest rank going to the subject with the lowest score, and the lowest rank going to the subject with the highest score. Tied scores result in a DOOR equal to the mean of the tied ranks. The algorithm is exemplified below using a simple scenario with 4 subjects.

Suppose Subject A has an OCO of 1 and 5 days of antibiotic use in the study period (score=1.05), Subject B has an OCO of 1 and 0 days of antibiotic use (score=1.00), Subject C has an OCO of 2 and 0 days of antibiotic use (score=2.00), and Subject D has an OCO of 1 and 5 days of antibiotic use (score=1.05). Because Subject B has the lowest score, Subject B is given DOOR=1 (the highest rank). Because Subject A and Subject D tie for the next lowest score, they both receive the mean of the next 2 available ranks (2 and 3, which has mean 2.5), and so the DOOR for both Subject A and Subject D is 2.5. Finally, Subject C has the highest score and therefore receives the worst available rank, which is DOOR=4.

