8.3.8. New occurrence of Fever at D11V Using ATP-11 Analysis Population

Using ATP-11, a forest plot of 95% CIs for the risk difference of fever in the 24 hours preceding or at D11V will be provided in [Figure 15](#). Results of fever at D11V will also be reported in [Table 45](#). Tests for differences in proportions between treatment arms will be given by Fisher's exact tests. The Miettinen–Nurminen method will be used to compute all 95% CIs for risk differences.

8.3.9. Bivariate Analysis of DOOR and Number of Days of Antibiotics Use at D5V and D11V

In addition to the DOOR analyses described in Section 8.2.8, a two-dimensional analysis of the DOOR probability and difference in the mean duration of antibiotic use in the two treatment groups will also be performed at D5V. Only subjects with non-missing DOOR and number of days on antibiotics will be included in these analyses. The horizontal axis is the DOOR probability (probability of a more desirable outcome when assigned to placebo vs. azithromycin) based on the ordinal DOOR outcome ignoring the duration of antibiotic use. The vertical axis is the difference in the means of the observed (outcome not assignment) duration of antibiotic use (placebo minus azithromycin). A result in the lower right quadrant represents more desirable results for placebo, while a result in the upper left represents more desirable for azithromycin. The other two quadrants represent tradeoffs for clinical outcomes and antibiotic use.

1000 bootstrap samples will be generated by resampling with replacement from the empirical distribution of DOOR and number of days of antibiotics use at D5V. The DOOR probability and mean difference in the number of days of antibiotics use will be estimated using the bootstrap samples and plotted as a scatter plot. A 95% joint region of DOOR probability and duration for antibiotic will be constructed first using a parametric method and repeated using a nonparametric method. The parametric method will estimate the confidence region using the ellipse method from the CAR R package which uses a bivariate normal distribution. The nonparametric will use distribution-free approach implemented in the distfree.cr R package proposed by Hu and Yang (2013) in [12]. Marginal distributions of DOOR probability and difference in duration of antibiotics will be provided. To confirm the robustness of these results, these plots will be regenerated using 2000

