Figure 13: Forest Plot of Risk Difference, Placebo Group Relative to Azithromycin, of Deterioration in the Symptom or Sign on Day 11 - ATP-11 Population

Figure 14: Forest Plot of Risk Difference, Placebo Group Relative to Azithromycin, of New Occurrence of Vital Sign Abnormality on Day 5 - ATP-5 Population

[figure not shown]

Figure 15: Forest Plot of Risk Difference, Placebo Group Relative to Azithromycin, of Fever on Day 11 - ATP-11 Population

[figure not shown]

Figure 16: Distribution of Ordinal Clinical Outcome Used for DOOR by Treatment Group and Timepoint

[figure not shown]
[figure not shown]

Figure 17: Cumulative Distribution Function for Ordinal Clinical Outcome Used for DOOR by Treatment Group at D5V - ITT Population

[Implementation note: Subjects with missing OCO will be excluded from this plot. 95% confidence bands will be added to the plot. Pseudocode: <https://communities.sas.com/t5/SAS-Programming/Add-upper-and-lower-confidence-limit-CDF-curves/m-p/316651#M69236>]

Figures with similar format:

Figure 18: Cumulative Distribution Function for Ordinal Clinical Outcome Used for DOOR by Treatment Group at D5V - ATP-5 Population

Figure 19: Cumulative Distribution Function for Ordinal Clinical Outcome Used for DOOR by Treatment Group at D11V - ITT Population

Figure 20: Cumulative Distribution Function for Ordinal Clinical Outcome Used for DOOR by Treatment Group at D11V - ATP-11 Population

Figure 21: Bivariate Analysis of DOOR at D5V - ITT Analysis Population with Complete Data at D5V

[Implementation Note: This figure will have 4 panels; the rows will represent the number of bootstrap samples (1000, 2000) and the columns will represent the parametric vs non-parametric approach. The ellipse function from the CAR package will be used to estimate the confidence regions using the parametric method and the distfree.cr R package for the distribution free approach will be used to estimating confidence regions. Marginal distributions of difference in duration of antibiotics use and DOOR probability will be added to the plot. This figure will be generated only if the variability in the number of days of antibiotic use justifies making such a figure.]

[figure not shown]

Figure with similar format:

Figure 22: Bivariate Analysis of DOOR at D11V - ITT Analysis Population with Complete Data at D11V

Figure 23: Distribution of Daily Ordinal Clinical Outcomes from Study Day 1 to Study Day 11 by Treatment Group and Timepoint - ITT Population

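### The DOOR tests at Day 5 and Day 11 break ties on antibiotic days, which nearly reproduce the randomised arm, so a significant result favouring placebo is not by itself evidence on clinical efficacy

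*SAP*

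**What the plan says.** Secondary objective 8 (SAP 3.1.2) compares the efficacy of the two arms "at Day 5 using a superiority approach, employing the RADAR methodology". Protocol 3.2.2 and SAP 3.3.5 define the endpoint as DOOR: patients are ordered by OCO, and then "When comparing two subjects with the same OCOs, the subject with fewer days of antibiotic use receives a higher rank". SAP 6.5.6 implements this with a score that "adds the number of days of antibiotic use (as defined in Section 6.5.5) divided by 100 to the OCO".

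SAP 6.5.5 counts a day as an antibiotic day if the patient took "any amount of study product that is not placebo, or any amount of other systemic antibiotic". SAP 4.4.1 gives one daily administration on each of Days 1 to 5. SAP 8.2.8 tests, at 0.05, whether the DOOR probability (placebo better, plus half of ties) is 50%, and describes 50% as no difference. SAP 8.3.3 repeats this at Day 11.

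The plan has some analyses without the tie-breaker:
- SAP 8.3.9 has an exploratory bivariate analysis in patients with complete data. One axis is a DOOR probability "based on the ordinal DOOR outcome ignoring the duration of antibiotic use". The implementation note to Figure 21 adds: "This figure will be generated only if the variability in the number of days of antibiotic use justifies making such a figure".
- SAP 8.3.10 has exploratory longitudinal DOOR tests without tie-breaking (Tables 53 to 55), with confidence intervals and p-values.
- Tables 49 to 51 give Wilson intervals for each OCO category within each arm.

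**The concern.** RADAR is informative when antibiotic duration is an outcome of a strategy and can vary in both arms. Here one arm is assigned a fixed five-day course and the other is assigned none. A placebo patient with no non-study antibiotic has 0 days. An azithromycin patient who took any dose has at least 1, and normally 5. Almost every cross-arm pair with the same OCO is therefore awarded to placebo by design. In ATP-5 the separation is tighter still, because membership requires five doses.

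Table 37 could thus show a significant result under an objective worded as efficacy when the two arms have identical clinical outcomes, or when placebo is clinically worse. What is at stake is how that secondary result is read.

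**Working it through.** **Sample size used.** The documents give no power or sample size for the DOOR test. The randomised number is reproduced by 560 / (1 − 0.169) = 673.9, so 674, or 337 per arm.

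**Other inputs.** Clinical improvement of 57.6% and the 12.5-point margin come from Protocol 11.1 and 11.2 and SAP 5. With placebo worse by the full margin, its rate is 57.6 − 12.5 = 45.1%. The split of patients within OCO 1–4 (improved) and 5–7 (not improved) is not in the documents, so it is assumed and varied.

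**Formula.** Let T be the probability that a random cross-arm pair has the same OCO, and θ the OCO-only probability (placebo better + T/2). If every tie goes to placebo, the planned DOOR probability is

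DOOR = θ + T/2.

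With identical clinical distributions θ = 0.5, so DOOR = 0.5 + T/2. This exceeds 0.5 whenever ties occur, and it holds at both visits.

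**Worked case (split 3 below, placebo 12.5 points worse).** The products for OCO 1 to 7 are:

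T = 0.4032×0.3157 + 0.1152×0.0902 + 0.0461×0.0361 + 0.0115×0.0090 + 0.3816×0.4941 + 0.0339×0.0439 + 0.0085×0.0110 = 0.330.

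P(placebo better) = 0.273, so θ = 0.273 + 0.165 = 0.437 after rounding, and DOOR = 0.273 + 0.330 = 0.602 from unrounded terms. The null standard error is √[675/(12×337²)] = 0.0223, or 0.0219 after the tie correction. Hence z = 0.102/0.0219 ≈ 4.7. The upper tail of F(1, ν) in SAP 8.2.8 is two-sided in direction, so the cut-off is close to 1.96.

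**Results at 337 per arm** (rejection means significant in favour of placebo):

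| Split: improved over OCO 1/2/3/4; not improved over 5/6/7 (%) | No difference: T | DOOR | Placebo −12.5: T | θ (OCO only) | DOOR | z | Rejection |
|---|---|---|---|---|---|---|---|
| 1. Improved/not improved only (limiting case) | 0.512 | 0.756 | 0.493 | 0.438 | 0.684 | 8.5 | ~100% |
| 2. 90/10/0/0; 90/8/2 | 0.419 | 0.709 | 0.403 | 0.438 | 0.639 | 6.4 | ~100% |
| 3. 70/20/8/2; 90/8/2 | 0.325 | 0.662 | 0.330 | 0.437 | 0.602 | 4.7 | 99.6% |
| 4. Azithromycin 60/25/12/3; 90/8/2. Placebo 70/20/8/2; 80/15/5 | 0.291 | 0.654* | 0.295 | 0.439 | 0.587 | 4.0 | 97% |
| 5. 25/25/25/25; all in OCO 5 | 0.263 | 0.631 | 0.298 | 0.438 | 0.586 | 3.9 | 97% |
| 6. 50/25/15/10; 70/20/10 | 0.212 | 0.606 | 0.215 | 0.438 | 0.545 | 2.05 | 53% |
| 7. 25/25/25/25; one third each | 0.143 | 0.571 | 0.143 | 0.437 | 0.509 | 0.40 | 6% |

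*Improvement rates are equal, but the assumed splits differ, so θ = 0.508.

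With equal improvement rates, rejection in favour of placebo is 90% in split 7 and over 99% in the others. At 280 per arm it is 84% in split 7 and at least 99% in split 6. On OCO alone at −12.5 points, the test points towards azithromycin and rejects in that direction in roughly 80 to 90% of simulated trials.

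**Imperfect separation.** Suppose 8% of placebo patients take five days of a non-study antibiotic and 3% of azithromycin patients take no dose, both independent of OCO. The tie term is multiplied by 0.92×0.97 − 0.08×0.03 = 0.89, so DOOR = θ + 0.445T. At −12.5 points this gives 0.437 + 0.147 = 0.584 (split 3), 0.438 + 0.096 = 0.534 (split 6) and 0.437 + 0.064 = 0.501 (split 7). In 1,000 simulated trials per case, placebo is favoured in 97% (split 3), 86% (split 5), 33% (split 6) and 4% (split 7). With equal improvement rates it is favoured in 81% (split 7) to 100%.

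**Day 11.** The assigned days are still 5 and 0. No Day 11 improvement rate is stated, so only the general result 0.5 + T/2 is claimed there. Non-study antibiotics between Days 5 and 11 would loosen the separation somewhat.

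**The case against.** The strongest defence is that the composite does what it was designed to do. Objective 8 names RADAR, the protocol defines DOOR with both ranking rules, and SAP 4.1 lists antibiotic usage among the efficacy outcome measures. A reader might infer that the test is invalid or cannot serve objective 8. The documents do not support that: crediting avoided antibiotics is its declared purpose. What remains is that a 50% null described as no difference does not separate clinical outcome from assigned exposure.

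The consequence is also contained. SAP 8.1.1 reserves the non-inferiority conclusion for the primary analysis. The Table 37 footnote says DOOR conclusions must also rest on the components and on sensitivity analyses, and several Day 5 components have between-arm intervals of their own. This limits the harm. But the ATP-5 and complete-data DOOR analyses keep the same tie-breaker, so they do not test this weakness.

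A reader might also infer that the plan contains no analysis free of the tie-breaker. That is wrong: Tables 49 to 51, Tables 53 to 55 and SAP 8.3.9 exist. However, the first are within-arm, the second combine time points, and the third is exploratory and conditional. A fixed course produces little within-arm variation in antibiotic days, so the condition on Figure 21 may fail in just the situation that makes the figure useful.

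Finally, the calculations assume complete data and do not model the multiple imputation, so the rejection rates are indicative and are not those of the Table 37 analysis.

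**Conclusion.** The point holds in a limited form. That the 50% null fails under identical clinical outcomes follows from the ranking and counting rules, and needs only that some pairs tie on OCO. Its size depends on the OCO split: DOOR is about 0.57 to 0.71 across the assumed splits (0.76 in the limiting case), with roughly 90 to 100% rejection at 337 per arm and full separation.

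A tempting stronger reading is that the test always declares placebo superior at the full 12.5-point deficit. The documents do not support that, because they give no OCO distribution. It is very likely where ties are about 30% or more (DOOR about 0.59 to 0.64, against 0.44 on OCO alone), about an even chance near 21%, and essentially absent near 14%. Nor is the statistic uninformative, since it falls as placebo worsens. The supportable conclusion is that a significant DOOR result is not by itself evidence on clinical efficacy, and that the plan does not assure the between-arm OCO-only result needed to read it. The primary analysis is untouched.

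**What to change.** - In SAP 8.2.8 and 8.3.3, add an OCO-only DOOR probability with 95% CI and p-value beside the tie-broken result in Tables 37, 38, 46 and 47, and in the complete-data Table 48.
- State how imputed OCO values are treated. SAP 8.4.2 imputes OCO by linear regression and gives no rounding rule, so fractional values would rarely tie with observed integers. Either specify a rule or restrict the added row to complete cases.
- Make the SAP 8.3.9 analysis (Figures 21 and 22) unconditional.
- Keep RADAR as the protocol-defined endpoint for objective 8. State that the tie-broken DOOR combines clinical outcome with antibiotic exposure, and that a significant result is not to be read as clinical efficacy superiority without the OCO-only result. Making OCO alone the deciding test would replace a protocol-defined endpoint and is not proposed.

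The cost is one extra row per table, a short rule for imputed values and two figures that are always produced, with no new data. The downside for the sponsor is a less favourable reading of the RADAR result.
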